4.1 Report Language

The TLFs as output of the analyses will be prepared in English.

4.2 Analysis Software

The statistical analysis will be performed using the SAS[®] statistical software package (Statistical Analysis System, Version 9.3 or later).

Pharmacokinetic derivations will be done using Phoenix WinNonlin 6.4 or later (Pharsight Corporation, Palo Alto, CA, USA) by a subcontractor

5 Data Preparation

5.1 Data Handling and Medical Coding

For data quality control and medical coding, please refer to the Data Management Plan, including the Data Validation Plan in its most recent version.

5.2 CDISC

All output as defined in the SAP will be generated based on CDISC ADaM datasets following ADaM implementation Guide 1.0, as per contract with Dompé farmaceutici S.p.A. SDTM programming will follow SDTM version 1.3 together with SDTM implementation guide 3.1.3.

Specifications for the ADaM datasets (as well as SDTM datasets) are described in a separate document.

5.3 SAS-Programming Quality Level

The following quality level of programming deliverables will be applied, as per contract with Dompé Farmaceutici S.p.A. All statistical output will receive a tailored Quality Control approach by:

- Full independently double programmed reproduction of CDISC:
 - o SDTM datasets
 - o ADaM datasets
 - o Tables and Figures
- Listings will not be double programmed.
- All tables, figures and listings will undergo comparison with specification (i.e. SAP and templates), cross checking with other tables and listings, a sensibility review and SAS-log review.

6 Analysis Sets and Subgroups

6.1 Analysis Sets

The Total Set (TOT) will include all subjects that have signed informed consent.

The Randomized Subjects Set (RAND) will include all subjects, which have been randomized to a study treatment.

If a subject is re-screened, the subject is formally dropped out of the study as screening failure and will be re-included with a new screening number. Details on re-screened subjects will be documented during the BDRM based on a detailed file note provided by clinical operations.

The Safety Set (SAF) will consist of all subjects randomized into the study and receiving a dose of study medication in at least one eye.

The PK-Set (PKS) will consist of all subjects who did not show serious protocol deviations or non-compliance and completed the PK sampling according to the study protocol.

All protocol deviations that occur during the study will be considered for their severity/impact and will be taken into consideration when subjects are assigned to analysis sets during a blind data review meeting (BDRM).

For the analysis of the SAF and PKS, summaries by treatment group (and eye) will follow the treatment a subject received.

Further analysis sets might be implemented during the BDRM, if deemed necessary as a consequence of treatment related protocol deviations.

6.2 Subgroup Definitions

No pre-planned subgroups.

7 Definition of Time Points and Analysis Variables

7.1 Definition of Time Points

The study consists of 12 scheduled clinical evaluation visits as described in Table 2.

The **Date of First Study Treatment** will be identified as the (earliest) date documented on the eCRF page “Administration of Study Drug” at D1 Visit, irrespective of the applied eye.

The **Treatment Day** of an event/assessment will be calculated relative to the First Study Treatment.

The Treatment Day of events/assessments occurring before the First Study Treatment will be calculated as:

- Treatment Day = (Date of assessment/event - Date of First Study Treatment).

For events/assessments occurring on or after First Study Treatment Administration, Treatment Day will be calculated as:

- Treatment Day = (Date of assessment/event - Date of First Study Treatment) + 1.

Relative Assessment Time of assessments is derived as the difference of the 24hr clock time on a respective day minus the time of the First Study Treatment at D1 Visit in hours utilizing 1 decimal. For example, if the time of First Study Treatment at D1 Visit was on 8:00 hr and the time of Baseline 0.5 hour was on 8:30 hr, then the Relative Assessment time will be 0.5 hours. So, the Relative Assessment Time is presenting the relative time within a visit day.

Relative Treatment Time Single Dose Scheme (hr) will be derived for all PK assessments and is defined as difference of the Date/Time of the assessment minus the time of First Study Treatment at D1 Visit in hours utilizing 1 decimal. For example, if the time of First Study Treatment at D1 Visit was on 8:00 hr and the time of D2 Pre-Dose was on 07:00 hr on the next day, then the Relative Treatment Time Single Dose Scheme will be 23.0 hours. So, the Relative Treatment time Single Dose Scheme presents the Time to First Study Treatment.

Relative Treatment Time Multiple Dose Scheme (hr) will be derived for all assessments on or after D2 and is defined as difference of the Date/Time of the assessment minus the time of First Study Treatment at D2 Visit in hours utilizing 1 decimal. For example, if the time of First Study Treatment at D2 Visit was on 8:00 hr and the time of D3 Pre-Dose was on 07:00 hr on the next day, then the Relative Treatment Time Single Dose Scheme will be 23.0 hours. So, the Relative Treatment time Multiple Dose Scheme presents the Time to First Study Treatment of the Multiple Dose Scheme.

For any subject discontinuing the study, the Investigator ask the subject to undergo, as far as possible, a final medical visit to examine the subject's health conditions

- a. *This examination will verify that all values tested at screening have remained within a clinically acceptable range (i.e., not clinically significant changes compared to screening). The assessments will be conducted as detailed in Follow Up Day 16±2 (FU 3).*
- b. *Arrange for alternative medical care of the withdrawn subject, if necessary*
- c. *Report in the eCRF date and time of the last dose administration, and date and primary reason of study discontinuation*
- d. *Record in the eCRF any follow-up, if the subject is withdrawn for an AE.*

Procedures conducted at the Early Termination Visit are at the discretion of the Investigator and may be among the study procedures or additional procedures not performed during the study but deemed necessary by the investigator.

All assessments except event type data will be analyzed according to the nominal visit identifier on the eCRF page, irrespective of meeting the time window as specified in the study plan and of having the procedures performed over 1 or 2 consecutive days.

This rule does not hold for subjects, who terminate study prematurely. For these subjects, the records collected at the Early Termination Visit will be shifted to the next applicable visit assessment according to Table 2. If this is not possible, the last record will be treated as Unscheduled Assessments based on the rules below.

Unscheduled Assessments will not be considered for by-visit analyses but all collected data will be listed. Additional assessments at a given visit will be labelled under the respective Visit label. However, the respective timepoint will be labelled as “xx hr U1”, “xx hr U2”, etc. with xx indicating the number of the last scheduled assessment time before the unscheduled assessment plus a consecutive sequence number.

Unscheduled Assessments which were not taken on a scheduled visit will be labelled as “Unscheduled Visit x.01 U1”, “Unscheduled Visit x.02 U1”, “Unscheduled Visit y.01 U1” etc. indicating the number of the last preceding visit plus a consecutive sequence number. If more than one unscheduled assessment is done at the same day, the assessments will be labeled consecutively “Unscheduled Visit x.01 U1”, “Unscheduled Visit x.01 U2”.

The **Treatment Period** starts with the first intake of study medication and ends before the first assessment of the D7 visit. Any assessment before the first intake of study medication is allocated to the **Screening Period**. The **Follow-Up Period** of the study will start with the first assessment on the D7 visit.

Moreover, the Treatment Period is divided into **Treatment Period of the Single Dose Scheme**, which ends before the first intake of study medication on D2 and the **Treatment Period of the Multiple Dose Scheme**, which starts with the first intake of study medication on D2.

If not stated otherwise in subsequent sections, Baseline is defined as the first assessment of the D-1 Visit.

Change from Baseline is defined as the difference between an assessment and the respective first assessment at the Baseline Visit.

Change from Multiple Dose Baseline is defined as the difference between an assessment and the respective Pre-Dose assessment at the D2 Visit.

A **Time-Matched Change from Baseline** is defined as the difference between an assessment and the respective assessment at the corresponding time-point at the Baseline Visit.

Table 2: Study Visits

Scheduled Visit	Scheduled Visit Label	Scheduled Relative Assessment Times within Visit	Comments
Screening Visit	Screening	Before Baseline Visit	Acceptable time window for screening visit: Treatment Day -21 to Treatment Day -2
Baseline Visit	D-1	0 hr 0.5 hr 2 hr 4 hr 8 hr 9 hr 10 hr 11 hr 12 hr 14 hr 16 hr	Acceptable time window: Day before first dose
Treatment Day 1	D1	Pre-Dose 0 hr 0.5 hr 2 hr 4 hr 8 hr 9 hr 10 hr 11 hr 12 hr 14 hr 16 hr	Dosing should occur at 0 hr Time of dosing should be identical to respective time point at baseline visit.
Treatment Day 2	D2	Pre-Dose 0 hr 0.5 hr 2 hr 4 hr 6 hr 8 hr 10 hr 10.5 hr 11 hr 12 hr 13 hr 14 hr 16 hr	Dosing should occur at 0, 2, 4, 6, 8, 10 hr. Time of dosing should be identical to respective time points at baseline visit.

Scheduled Visit	Scheduled Visit Label	Scheduled Relative Assessment Times within Visit	Comments
Treatment Day 3	D3	Pre-Dose 0 hr 2 hr 4 hr 6 hr 8 hr 10 hr	Dosing should occur at 0, 2, 4, 6, 8, 10 hr. Time of dosing should be identical to respective time points at baseline visit.
Treatment Day 4	D4	Pre-Dose 0 hr 2 hr 4 hr 6 hr 8 hr 10 hr	Dosing should occur at 0, 2, 4, 6, 8, 10 hr. Time of dosing should be identical to respective time points at baseline visit.
Treatment Day 5	D5	Pre-Dose 0 hr 2 hr 4 hr 6 hr 8 hr 10 hr	Dosing should occur at 0, 2, 4, 6, 8, 10 hr. Time of dosing should be identical to respective time points at baseline visit.
Treatment Day 6	D6	Pre-Dose 0 hr 2 hr 4 hr 6 hr 8 hr 10 hr 10.5 hr 11 hr 12 hr 13 hr 14 hr 16 hr	Dosing should occur at 0, 2, 4, 6, 8, 10 hr. Time of dosing should be identical to respective time points at baseline visit.
Follow-up Visit 1	FU1	0 hr	Acceptable time window: treatment day 7 Assessment times should be identical to respective time points at baseline visit.
Follow-up Visit 2	FU2	0 hr 8 hr	Acceptable time window: treatment day 8 Assessment times should be identical to respective time points at baseline visit.

Scheduled Visit	Scheduled Visit Label	Scheduled Relative Assessment Times within Visit	Comments
Follow-up Visit 3	FU3	0 hr	Acceptable time window: treatment day 14-18 Assessment times should follow respective time point at baseline visit.
Follow-up Visit 4	FU4	0 hr	Acceptable time window: treatment day 35-42 Assessment times should follow respective time point at baseline visit.
Early Termination	ETV	-	Early termination visit.

7.2 Analysis Variables

This section describes all variables that are used for analysis as well as their source data variables. For each variable it is specified how missing values will be handled, if applicable.

7.2.1 Disposition and Protocol Deviations

Disposition parameters were recorded on the eCRF Page “End of Study”.

Study discontinuations were recorded for all subjects who provided informed consent.

A subject discontinued the study prematurely, if the question “Did the subject complete the study” was answered as ‘No’. A subject is considered as study completer, if the question “Did the subject complete the study” was answered as ‘Yes’.

Primary Reason for Study Discontinuation is documented on the eCRF Page “End of Study” in categories ‘Adverse Event’, ‘Lost to Follow-Up’, ‘Decision unrelated to an Adverse Event’, ‘NonCompliance’, ‘Study terminated by the sponsor’, ‘Study terminated by the investigator’, ‘Other’.

If the eCRF question “Was the emergency envelope opened during the study?” was answered ‘Yes’, the subject will be considered as unmasked.

The eligibility of all subjects for entry into the study will be assessed at the Screening visit and confirmed at the Baseline Visit on the eCRF Pages “Inclusion Criteria” and “Exclusion Criteria”.

Protocol deviations were collected during the study and reviewed during the BDRM according to a separate BDRM plan. During the BDRM, identification of protocol deviations and further categorization of deviations for TLF output will be performed. For the analysis, all protocol deviations as documented in the BDRM minutes will be presented.

7.2.2 Demographics and Other Baseline Characteristics

Demographics

Demographic characteristics were recorded on the eCRF page “Demography”.

Gender (‘Male’, ‘Female’), Ethnicity (‘Japanese’, ‘Not Japanese’), All 4 Grandparents born in Japan (‘Yes’, ‘No’) will be analyzed as recorded on the eCRF.

Age (years) at Screening is calculated as:

- $\text{INT}((\text{date of informed consent} - \text{date of birth})/365.25)$.
In case of incomplete dates, missing days will be set to 1st and missing months will be set to July.

Other Background Information

Body height and weight are recorded on the eCRF page “Vital Signs” at the Screening Visit.

Based on this, the BMI (kg/m^2) at Screening is derived as $\text{Weight at Screening (kg)} / (\text{Height at Screening [cm]} * 0.01)^2$. BMI will be presented with 1 decimal of precision.

Smoking habits and alcohol consumption are recorded on the eCRF page “Demography” at Screening Visit.

For the analysis, the number of alcohol units will be presented. For this, subjects who answered the question “Is the subject an alcohol consumer” with ‘No’ will be imputed by 0 alcohol units.

An alcohol breath test is performed at Screening and Baseline Visit and is recorded on the eCRF page “Alcohol Breath Test”.

An urine drug screening is performed at Screening and Baseline Visit and is recorded on the eCRF page “Drugs of Abuse”.

Medical history and other medical conditions

The study eye (‘Left Eye’, ‘Right Eye’) as randomized will be presented according to the assigned randomization number on the eCRF page “Randomization”.

Schirmer’s tear test assessing the wetting distance at 5 min (mm) is performed at Screening and Baseline Visit and is recorded on the eCRF page “Schirmer Tear Test”.

Medical history is recorded on the “Medical history” eCRF page. Medical history contains information about conditions that a subject might have suffered prior to Screening Visit, or conditions that are ongoing at the time of the Screening Visit. The medical history terms as specified by the investigator will be coded to a Preferred Term (PT) and a System Organ Class (SOC) using the Medical Dictionary for Regulatory Activities (MedDRA) thesaurus.

If no coding information will be available for a specific medical history record, the record will be presented as ‘Uncoded Record’. However, for final TLFs it is anticipated that all medical/surgical history records are coded.

For females, a serum pregnancy test was performed at Screening and a urine pregnancy test is performed at Baseline Visit. Both tests are documented on the eCRF pages “Serum/Urine Pregnancy Test”, respectively.

At Screening Visit, a test for Hepatitis B antigen (HB_sAg) and Hepatitis C antibodies (HCV) as well as a combined screening test for HIV1 and HIV2 was performed in blood serum and documented on eCRF page “Serology”.

7.2.3 Prior/Concomitant Medication

Prior and Concomitant medication data will be collected throughout the study on the “Prior / Concomitant Medications” eCRF page.

All medications (including over-the-counter drugs, herbal products, vitamins, and antacids) taken within 4 weeks prior to the start of and throughout the study must be recorded on the case report form. The use of the medications with exclusion periods before dosing longer than

4 weeks will only be checked at Screening for eligibility but would need not to be otherwise recorded.

All medications will have a calculated start and stop day to enable categorization of the medications as 'Prior' or 'Concomitant':

- Start Day is defined as:
 - Start Date of Medication – Date of First Study Treatment + 1
If the Start Date of the Medication is greater than or equal to the Date of First Study Treatment (see section 7.1)
 - Start Date of Medication – Date of First Study Treatment
If the Start Date of the Medication is less than the Date of First Study Treatment.
- Stop Day is defined as:
 - Stop Date of Medication – Date of First Study Treatment + 1
If the Stop Date of the medication is greater than or equal to the Date of First Study Treatment
 - Stop Date of Medication – Date of First Study Treatment
If the Stop Date of the Medication is less than the Date of First Study Treatment.

'Prior medications' are medications that were started before and stopped before or on the day of First Study Treatment Administration.

'Concomitant medications' include all medications that a subject used during the Treatment or Follow-Up Period of the study.

Any medication started prior to first study treatment, which was not discontinued on/before Date of First Study Treatment, will be considered as 'Concomitant'. Moreover, any medication started at any time after the First Study Treatment will be considered 'Concomitant'.

Medications started and stopped on the day of First Study Treatment will be considered to be 'Concomitant'.

The Investigator Terms (Medication Name, and Indication) will be coded to a World Health Organization Anatomical Therapeutic Chemical (WHO-ATC) Drug class, a WHO-ATC Drug number and a WHO Drug Name (Preferred Term) using the WHO-DRL Drug Dictionary.

Missing Codes or Medication Dates Imputation:

In the event that coding information will not be available for a specific concomitant medication, the concomitant medications will be presented as 'Uncoded Medication'. However, for final TLFs it is anticipated that all medication records are coded.

Missing and/or incomplete dates for prior and concomitant medications will be imputed for calculating relative start and stop days only. Dates will be listed as missing/incomplete [with "-" replacing missing information] but the Start/Stop Day listed between square brackets to denote it was calculated based on missing data (i.e. [-28], [1], [Ongoing]).

Missing and/or incomplete dates will be imputed in a manner that assumes the worst case scenario.

Technically, incomplete stop dates will be imputed as follows:

- For a missing day (but month and year is available), it will be assumed that medication have been stopped on the last day of the respective month.
- For a missing month (but year is available), it will be assumed that medication have stopped on 31st December of the respective year.
- For a completely missing stop date, the medication will be assumed to be ongoing.

Similarly, incomplete start dates will be imputed as follows:

- For a missing start day (but month and year is available), onset is assumed on the first day of the respective month.
- For a missing start month (but year is available), onset is assumed on 1st January of the respective year.
- For a completely missing start date, no imputation is performed. However, the medication will be considered as concomitant, unless indicated different by stop date.

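### SAP 7.2.3 classes a medicine started before D1 and stopped on D1 as Prior only, even if it was taken after the first drop, against the section's own definition of Concomitant

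*SAP*

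**What the plan says.** SAP 7.2.3 derives a start day and a stop day for every medication and uses them to sort each record into Prior or Concomitant. Four statements bear on a stop date of D1:

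- The Prior class covers "medications that were started before and stopped before or on the day of First Study Treatment Administration".
- By the general definition, the Concomitant class is to "include all medications that a subject used during the Treatment or Follow-Up Period of the study". Under SAP 7.1 that first period "starts with the first intake of study medication and ends before the first assessment of the D7 visit".
- A medicine begun before first treatment, "which was not discontinued on/before Date of First Study Treatment, will be considered as 'Concomitant". One that was discontinued on that date therefore does not qualify under this rule.
- The same-day rule reads: "Medications started and stopped on the day of First Study Treatment will be considered to be" Concomitant.

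SAP 10.4.3 and the table list in SAP 12 summarise the two classes separately, in Table 14.1-6.1 (Prior) and Table 14.1-6.2 (Concomitant). They are counted per subject and by treatment group on the Safety Set. Listing 16.2.05-1.1 gives all documented medications with a Prior flag. Protocol 8.3 asks for a start date and a discontinuation date for each medicine and lists no clock time.

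**The concern.** The general definition of Concomitant turns on use after the first drop. The date rules turn on the calendar date of stopping. For a medicine taken from D-1 to the evening of D1 they give opposite answers, and the SAP does not say which prevails. If the date rules are programmed, which is the natural reading because they are the operational ones, that medicine is missing from Table 14.1-6.2 although it was used under treatment.

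D1 is also handled in two opposite ways. A single intake early on D1, before the drop, is Concomitant because it started and stopped that day. A course begun the day before and finished after the drop is Prior.

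What is at stake is the description of co-medication during the single-dose scheme. That scheme has its own primary adverse-event endpoint (SAP 7.2.6) and its own tolerability assessments, including the D1 8 h VAS (SAP 7.2.7). The protocol's general rule is that no other medicine is given (Protocol 5.7). I take it as likely, though the documents do not say so, that a reader will use the concomitant table to see what else subjects took while treated.

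**Working it through.** There is no planned figure to reproduce, so the check applies the SAP's rules to start and stop patterns around D1.

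Inputs:
- Start and stop day (SAP 7.2.3): date minus date of first treatment, plus 1 if on or after that date.
- Prior: start before the D1 date and stop on or before the D1 date.
- Concomitant by the date rules: started earlier and not stopped by the D1 date, or started and stopped on D1, or started after first treatment.
- Use in the Treatment Period (SAP 7.1): any intake from the first drop on. The first drop is assumed at 08:00, the time used in the SAP 7.1 examples.

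| Start | Stop | Start day / stop day | Prior | Concomitant by date rules | Used in Treatment Period |
|---|---|---|---|---|---|
| 3 days before D1 | D-1 | -3 / -1 | yes | no | no |
| 3 days before D1 | D1, before drop | -3 / 1 | yes | no | no |
| 3 days before D1 | D1, after drop | -3 / 1 | yes | **no** | **yes** |
| 3 days before D1 | D2 | -3 / 2 | no | yes | yes |
| D1 | D1, after drop | 1 / 1 | no | yes | yes |
| D1 | D1, before drop | 1 / 1 | no | yes | no |
| D1 | D3 | 1 / 3 | no | yes | yes |

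Only the third row has use under treatment without the concomitant class. Rows two and three have the same start and stop days, so recorded dates cannot separate them. Row six errs the other way and is counted as Concomitant although use ended before the drop.

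Size per affected subject, assuming all randomised subjects are dosed (20 rhNGF, 10 vehicle):
- rhNGF: 1/20 = 5 percentage points.
- Vehicle: 1/10 = 10 percentage points.
- Overall column: 1/30 = 3.3 percentage points.

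These are maxima for the row counting subjects with at least one concomitant medication. Counting is per subject, so a subject with any other concomitant medicine is already in that row and it does not move.

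Can the pattern occur? Protocol 5.7 permits limited paracetamol or ibuprofen, up to 3 consecutive days, so a course from D-1 to D1 is possible. The synopsis also permits medication to treat adverse events, and these are recorded from consent (Protocol 9.2). The documents give no count.

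**The case against.** The case against acting is mostly about consequence, and much of it stands. The two date-based sentences agree with each other, so a programmer can apply them without ambiguity. The protocol restricts medication before and during the study, and subjects are resident from D-1 at the latest, so the pattern should be uncommon. The analysis is purely descriptive, and no endpoint, PK parameter or analysis-set definition uses the flag. Because only dates are requested, any date rule will misplace some medicines stopped on D1. None of this removes the conflict with the general definition or the opposite treatment of same-day medicines.

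Some stronger readings are tempting but unsupported:

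- A reader might infer that the concomitant table misses drug use in the single-dose window generally. It does not: medicines started on D1, or continued beyond it, are counted.
- A reader might infer that affected medicines are reported as finished before treatment. The Prior definition openly includes stops on the day of treatment, and the record remains in Table 14.1-6.1 and the listing.
- With an 08:00 drop, 16 of the 24 hours to the first D2 dose (16/24 = 67%) fall on the D1 date. That is a share of clock time. It does not measure omitted use, since other medicines taken in those hours are counted.
- A reader might say the rule breaks the SAP's worst-case principle: "Missing and/or incomplete dates will be imputed in a manner that assumes the worst case scenario". That sentence covers missing or incomplete dates only. Nor does it always push towards Concomitant: setting a missing start day to the first of the month can move a record with a D1 stop into Prior.

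**Conclusion.** The inconsistency is real and confined to one pattern: start before D1, stop date exactly D1, last intake after the drop. Under the date rules such a record is absent from Table 14.1-6.2, contrary to the section's own definition of Concomitant. The size is unknown and probably small, with the 5-point and 10-point figures as upper limits per affected subject. The conclusion assumes that programming follows the date rules. If the general definition were taken to prevail, the record would be counted, but the SAP does not state this, and dates alone do not show whether use continued after the drop. The point concerns the accuracy of one descriptive table. It does not affect the validity of the safety, tolerability or PK results. It is worth correcting because the stated rule misclassifies these records and the correction is simple.

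**What to change.** In SAP 7.2.3:

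1. Define Prior as stopped before the Date of First Study Treatment, by deleting *or on the day of* from the Prior definition.
2. In the paragraph on medicines begun before first treatment, change *on/before* to *before*.
3. State that every medication that stopped on or after that date, is ongoing, or started on or after that date is Concomitant.

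The two classes then exclude each other, and the same-day sentence follows from the rule. The cost is two wording edits, one clarifying sentence and one changed programming condition, with no new data. The downside is that a medicine begun earlier and last taken before the drop on D1 is also counted as Concomitant. The SAP already accepts the same over-counting for medicines started and stopped on D1, and the listing still shows the stop date.
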